We plan to enroll 67 children with hematologic malignancies (including acute myeloid leukemia, acute lymphoblastic leukemia, juvenile myelomonocytic leukemia, and myelodysplastic syndrome) at the time of HSCT at three institutions (including UCSF, All Children's Hospital, St. Petersburg, FL, and Lucile Packard Children's Hospital, Palo Alto, CA). Patients will be enrolled on the study by day +28, prior to withdrawal of immunosuppression or administration of donor lymphocyte infusion (DLI). They will have donor chimerism and minimal residual disease (MRD) testing from the peripheral blood (PB) and bone marrow (BM) on day $+28 \pm 7$ (as per standard of care). Based on risk assessment, patients will receive one cycle of low-dose azacitidine ($40\text{mg}/\text{m}^2$ IV/SC daily $\times 4$ days) alone as immunosuppression is tapered. After tapering immunosuppression, chimerism will be repeated and patients will receive up to 6 additional cycles of low-dose azacitidine. For patients who meet at high risk for relapse, azacitidine will be combined with escalating doses of DLI for a maximum of 7 cycles in total. Risk and safety assessments, including routine laboratory parameters, donor chimerism, minimal residual disease, and GHVD activity will be assessed following each cycle.

The primary outcome measures will be indicators of relapse risk and safety / toxicity. Patients will be followed for relapse as well as incidence of severe drug toxicities and acute and chronic GVHD until 2 years post-transplant. The study will be considered successful if the rate of relapse at 2 years is $<25\%$, and the incidence of Grade IV GVHD and severe drug toxicity are $<20\%$. Correlative studies will include the effect of azacitidine on T cell immune reconstitution, as well as prospective minimal residual disease estimation by gene expression / mutation panels in patients with AML.

Study Schema

Standard Risk:

- Active Grade I GVHD, OR
- Any history of >Grade II GVHD, OR
- Full Donor Chimerism AND Pre-HSCT MRD-neg AND Post-HSCT MRD-neg

High Risk:

- No GVHD or resolved Grade I GVHD, AND
- Mixed chimerism OR Pre-Tx MRD(+) OR Post-Tx MRD(+)

[figure not shown]

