3.0 Study Design and Eligibility Criteria

3.1 Study Design (see also Study Schema, page 3)

- 3.1.1 We propose a Phase II single-arm trial of azacitidine (IV or SC) in combination with escalating donor lymphocyte infusions (DLI). This study will be open to patients with ALL, AML, JMML, or MDS.
- 3.1.2 The first cycle of azacitidine will be administered during withdrawal of immunosuppression for patients not developing severe organ toxicity or Grade III-IV GVHD.
- 3.1.3 After the initial cycle during withdrawal of immunosuppression (duration is based on day 28 PB chimerism), azacitidine is given for 4 days in 6-week cycles (+/- 2 weeks) at a dose of 40 mg/m²/day.
- 3.1.4 For patients meeting High Risk criteria who have available cell product, DLI is given on day 5 of each cycle in escalating doses. Peripheral blood chimerism and MRD is assessed after week 4, prior to initiating the next cycle. BM chimerism and MRD is

obtained at regular intervals prior to specified cycles as per the study schedule. Patients will receive up to 7 cycles as tolerated.

3.1.5 Patients will be followed by laboratory monitoring and physician evaluation prior to each cycle. Weekly labs will be obtained and will include toxicity monitoring (CBC, LFTs, and electrolytes) and correlative studies, such as immunophenotype and T cell function by PHA. Patients will be followed for two years to study toxicity and GVHD outcomes as well as relapse incidence.

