3.3.1 Patients who have had a prior transplant

3.3.2 Patients receiving a haploidentical/T cell depleted transplant

3.3.3 Patients with Fanconi anemia or other cancer-predisposition syndromes

3.3.4 Patients with expected survival <12 weeks

3.3.5 Lansky score <60%

4.0 Patient Registration

4.1 Recruitment:

Patients will be recruited to the study by a bone marrow transplant physician during pre-transplant clinic visits, or during hospital admission. Patients will be consented for study any time between pre-transplant consent conference and day +28; enrollment will occur before day +28 and prior to withdrawal of immunosuppression.

4.2 Registration:

All prospective patients will undergo an informed consent conference during which their transplant physician will explain risks, benefits and alternatives to the study participation. The assent of the recipient will be obtained when age appropriate, as well as parental permission. To register patients, the attending physician will contact the Study Chair, [REDACTED]

[REDACTED] The investigator will complete the eligibility forms (provided in the Case Report Form packet) and fax them per the instructions on the form to either the UCSF PI or UCSF Study Coordinator. Pertinent information will be maintained at UCSF on each enrolled patient.

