7.0 Criteria for Termination

7.1 Conditions for terminating the study:

The PI may terminate the study for any of the following reasons:

- 7.1.1 Significant toxicities are observed.
- 7.1.2 Stopping rules for interim toxicity and relapse futility are triggered as per Section 8.7.3.
- 7.1.3 It becomes clear that the study treatment is less effective than standard treatment.
- 7.1.4 All data have been collected.

7.2 Conditions for terminating individual patient participation in the study:

The PI may terminate the participation of an individual patient for any of the following reasons:

- 7.2.1 Withdrawal from the study by patient / parents or physician
- 7.2.2 Death
- 7.2.3 Leukemia relapse, defined as >5% leukemic blasts on bone marrow examination or more than 1% leukemic cells by immunoflow or FISH.
- 7.2.4 Loss to follow-up or non-compliance with study procedures.

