8.4 Sample size

- 8.4.1 The sample size is estimated using Bayesian sequential monitoring design with toxicity and response outcomes as multiple endpoints(45). It is assumed that the rate of relapse in pediatric acute leukemia post-transplant would be 40% (as shown in our pilot study), azacitidine +/- DLI would reduce the 2-year relapse rate by approximately 40% to a rate of 25%. A sample size of 67 evaluable patients is required to provide 80% power at a one-sided significance level of 0.05 to test the hypothesis based on the relapse rate of H0: relapse rate > 40% (historically-controlled) versus Ha: relapse rate < 25% (treatment-targeted). The study will enroll patients until accrual of 67 patients is achieved.
- 8.4.2 Enrollment of 67 patients will be attainable with enrollment at multiple centers. Investigators from All Children's Hospital, Lucille Packard Children's Hospital have written letters of support expecting to enroll 30-40 patients over 2 years.

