8.6 Statistical Analysis

- 8.6.1 Patient demographics and baseline characteristics including age, sex, race, ethnicity and medical conditions will be summarized using descriptive statistics. For quantitative parameters, descriptive statistics will include the mean, standard deviation, minimum, median and maximum. For qualitative parameters, descriptive statistics will include the frequency and proportions.
- 8.6.2 The primary endpoint parameters: (1) relapse rate and (2) incidence of Grade III-IV aGVHD, severe cGVHD, and Grade IV toxicities, will be estimated using proportions with 95% CI.
- 8.6.3 The chimerism parameters (CD3+, CD14/15+, CD19+, CD33+, CD34+) and incidence of acute and chronic GVHD will also be analyzed using descriptive statistics including means, standard deviation and 95% CI.

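### Section 8.6.2 estimates two-year relapse as a simple proportion with no rule for patients who leave early; a cumulative incidence at 24 months post-transplant would handle them

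*Combined protocol and SAP*

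**What the plan says.** The trial has one arm (section 3.1), and section 8.1 defines the primary efficacy endpoint only as relapse rate, with no time point, censoring rule or competing event. The protocol summary supplies the horizon: "The study will be considered successful if the rate of relapse at 2 years is" below 25%. Section 8.4 sets up a test of "H0: relapse rate > 40% (historically-controlled) versus Ha: relapse rate < 25% (treatment-targeted" with "80% power at a one-sided significance level of 0.05", and states "A sample size of 67 evaluable patients is required". Accrual also stops at 67, so there is no allowance for loss, and *evaluable* is not defined.

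The only estimator is in section 8.6.2: the primary parameters "will be estimated using proportions with 95% CI". No time-to-event method is named anywhere, even for the secondary endpoints of relapse-free survival and median time to relapse (section 8.2).

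Section 7.2 lists reasons for ending a patient's participation. They include withdrawal by family or physician, death, and "Loss to follow-up or non-compliance with study procedures". Section 5.7 sends two further groups to separate safety and efficacy analyses: patients whose azacitidine is held for more than six weeks, and patients given DLI without azacitidine in cycles 2 to 7. It does not say whether they stay in the primary denominator.

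On timing, section 4.1 says "enrollment will occur before day +28 and prior to withdrawal of immunosuppression", while follow-up (section 5.12) and adverse event reporting (section 11.12) run to two years post-transplant.

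**The concern.** A proportion observed at two years is well defined only when every patient's two-year status is known. For someone last seen relapse-free at eight months there are three simple choices: count as relapse-free, drop, or count as relapsed. The plan makes none of them. In an open single-arm trial against a fixed benchmark, that choice could be made after the results are visible.

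A small shift matters because the target and the success line are both 25%. Suppose 16 relapses are seen and 7 of the 67 patients are lost relapse-free. Kept in the denominator, the rate is 16/67 = 23.9%, a success. Dropped, it is 16/60 = 26.7%, a failure. Counted as relapsed, it is 23/67 = 34.3%.

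Death without relapse also needs to be visible, because it removes patients from risk of relapse. Section 8.7.3 cites GVHD-related mortality of 5% to 15% after DLI.

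**Working it through.** **1. The plan's own figure.** Inputs from section 8.4: p0 = 0.40, p1 = 0.25, one-sided alpha 0.05, power 80%.

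- Normal approximation: n = [(1.645·√0.24 + 0.842·√0.1875)/0.15]² = 60.9. With continuity correction it is 67.4, close to the stated 67.
- Exact binomial at n = 67: P(X ≤ 19 | 0.40) = 0.032 and P(X ≤ 20 | 0.40) = 0.056. The largest cut-off that respects alpha 0.05 is therefore 19, with power P(X ≤ 19 | 0.25) = 0.784. The plan does not state this cut-off.
- Literal success criterion: below 25% of 67 means at most 16 (16/67 = 23.9%; 17/67 = 25.4%). P(X ≤ 16 | 0.40) = 0.004.

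**2. Model for early exit.** The assumptions are constant hazards, death without relapse D = 10% by two years, and loss L = 5% to 20% by two years, independent of relapse. With two years as the time unit and true relapse F:

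- λ_relapse + λ_death = −ln(1 − F − D), split in the ratio F : D.
- λ_loss = −ln(1 − L).
- With S the sum of the three hazards and c = (1 − e^(−S))/S, the proportion seen to relapse is λ_relapse·c and the proportion lost first is λ_loss·c.

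**3. Bias at a true rate of 25%.** Here λ_relapse = 0.308 and λ_death = 0.123. At L = 10%, λ_loss = 0.105, S = 0.536 and c = 0.774. Seen to relapse: 0.308 × 0.774 = 23.8%. Lost first: 8.2%. If the lost are dropped: 0.238/(1 − 0.082) = 25.9%.

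| Loss by 2 years | Lost counted relapse-free | Lost dropped | Lost and dead dropped | Cumulative incidence, death competing |
|---|---|---|---|---|
| 0% | 25.0% | 25.0% | 27.8% | 25.0% |
| 5% | 24.4% | 25.4% | 28.3% | 25.0% |
| 10% | 23.8% | 25.9% | 28.9% | 25.0% |
| 20% | 22.6% | 27.0% | 30.3% | 25.0% |

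The last column comes from 20,000 simulated trials of 67 patients, which also reproduce the other columns. One minus Kaplan-Meier with deaths censored is not a substitute: it gives 1 − e^(−0.308) = 26.5%.

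**4. One-sided error at a true rate of 40%, lost patients counted relapse-free.** The same model gives the proportion seen to relapse; the binomial gives the error.

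| Loss | Seen to relapse | P(X ≤ 19), implied test | P(X ≤ 16), literal criterion |
|---|---|---|---|
| 0% | 40.0% | 3.2% | 0.4% |
| 5% | 39.1% | 4.5% | 0.6% |
| 10% | 38.2% | 6.1% | 1.0% |
| 20% | 36.3% | 10.9% | 2.1% |

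**The case against.** Follow-up is meant to be complete: visits at least every three months for two years (section 5.12), and two years of data collection after two years of accrual (section 8.5). A binary endpoint at a fixed time is conventional in phase II and suits the count-based stopping rules in section 8.7. This stands to the extent that, with no loss and deaths kept in the denominator, the proportion and the cumulative incidence agree. The size of the problem depends entirely on loss, for which the documents give no figure.

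A reader might infer three stronger things that the documents do not support.

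- **That the bias favours success.** It does only if lost patients count as relapse-free. Dropping them pushes the rate up, against success, and the undefined word *evaluable* is at least as compatible with that.
- **That the trial's false-positive rate rises to 12% or 20%.** With 10% or 15% leaving early and every one of their relapses unseen, the observed rate would be 36% or 34%, and P(X ≤ 19) would be 11.9% or 20.0%. These are extremes, and they use the derived cut-off. At most 16 of 67 gives 2.4% and just under 5.0% in the same two cases.
- **That deaths alone invalidate the proportion.** They do not, unless the dead are dropped as not evaluable.

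Censoring is also no complete cure. It is unbiased only if exit is unrelated to relapse risk, and physician withdrawal or non-compliance may be related.

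**Conclusion.** The point holds as a recommended change, not a critical flaw. The plan names a simple proportion for a two-year endpoint, foresees exits before two years, and gives no rule for them. Under the stated assumptions (true rate 25%, 10% death, 5% to 20% independent loss), the choice of handling moves the estimate down by 0.6 to 2.4 points or up by 0.4 to 2.0 points, across the line that decides success. The error of the implied 19-of-67 test exceeds the planned 5% at 10% loss or more if lost patients count as relapse-free; the error of the literal below-25% criterion does not. Cumulative incidence removes this bias when loss is non-informative. The stated sample size is reproduced closely and is not in question here.

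**What to change.** In section 8.6.2, replace the proportion for relapse with the Aalen-Johansen cumulative incidence at 24 months post-transplant. Treat death without relapse as the competing event and censor early exits at last contact.

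- Count time from transplant, with delayed entry at enrolment for patients enrolled after transplant. The day +28 assessment would not work as time zero: it may fall from day +21 to day +42 (section 5.2.2), and 24 months from it runs past the required follow-up.
- Report the 95% CI, and base both the one-sided test against 40% and the below-25% criterion on this estimate.
- Show non-relapse mortality and relapse-free survival beside it.
- Define *evaluable*, and state whether the patients analysed separately under section 5.7 stay in the primary analysis.
- Add a sensitivity analysis that counts lost patients as relapsed.

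The cost is mainly wording and slightly more analysis work. Relapse and treatment-related death are already reportable (sections 11.14 and 11.16); no case report form is shown, so collection of a last-contact date should be confirmed. Precision falls a little: in the simulation at a true 25%, the standard deviation of the estimate rises from 5.3 points with no loss to 5.4 at 10% loss and 5.6 at 20%. The sample size need not change unless a loss allowance is added. The remaining downside is reliance on non-informative censoring, which the sensitivity analysis is there to probe.

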8.7 Interim analysis and stopping rules for safety and efficacy

- 8.7.1 As a phase II study with 67 evaluable patients, the study is designed to have interim stopping rules based on the safety/toxicity evaluation (including death and incidence of severe GVHD). See Section 11.0 for reporting SAEs associated with study stopping rules.
- 8.7.2 The occurrence of any serious adverse events (SAEs) will be reported to the Coordinating Trial Center within 24 hours of learning about them, and within 10 days in writing. See Section 11.0 for SAE definitions and reporting requirements. A rate of SAEs of up to 20% is deemed acceptable in view of the potential benefit of the therapy. Accrual will stop if 3 patients with SAEs are observed in the first 3-6 patients undergoing the intervention, if 4 patients with SAEs are observed in the first 7-9 patients undergoing the intervention, or if 5 patients with SAEs are observed in the first 10-13 patients undergoing the intervention. The following table displays the minimum

number of SAEs for the study to be stopped at each accrual period and the probability of early stopping at the assumed SAE rate.

Patients on Study	4-6	7-9	10-13	14-17	18-21	22-27
Number of patients with SAE	≥3	≥4	≥5	≥6	≥7	≥8
15%SAE	1.2%- 4.2%	1.1%- 2.8%	0.9%- 2.7%	0.9%- 2.4%	0.9%- 2.0%	0.8%- 2.6%
20%SAE	2.6%- 8.2%	2.9%- 6.6%	2.6%- 6.9%	3.2%- 6.8%	3.5%- 6.6%	3.6%- 8.2%
25%SAE	4.7%- 13.2%	5.8%- 11.7%	5.8%- 12.6%	7.3%- 12.8%	8.2%- 12.7%	8.9%- 14.2%

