5.6 Schedule of standard and fast withdrawal of immunosuppression (SWI versus FWI)

5.6.1 Standard withdrawal of immunosuppression will be performed per institutional standard procedure. Suggested course of taper is over 10 weeks starting at day 30-50.

5.6.2 Fast withdrawal of immunosuppression will be performed per institutional standard procedure. Suggested course of taper is over 2-4 weeks starting at day 30-50.

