8.5 Estimated Duration of the Study

- 8.5.1 67 patients are expected to enroll; enrollment over 2 years is anticipated. Study intervention and data collection (2 years) are expected to be completed by 4 years. Preliminary safety analysis will be available within 1 year.

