11.12 Adverse Events Reporting

The Study Chair will assess all adverse events and determine reportability requirements to the UCSF Data and Safety Monitoring Committee (DSMC) and UCSF's Institutional Review Board, and the Committee on Human Research (CHR). Adverse events will be reported to the DSMC via OnCore.[®]

All adverse events entered into OnCore[®] will be reviewed by the Helen Diller Family Comprehensive Cancer Center Site Committee on a monthly basis. The Site Committee will review and discuss monthly the selected toxicity, the toxicity grade, and the attribution of relationship of the adverse event to the administration of the study treatment.

All grade(s) 3-5 adverse events entered into OnCore[®] will be reviewed on a monthly basis at the Site Committee meetings. The Site Committee will review and discuss the selected toxicity, the toxicity grade, and the attribution of relationship of the adverse event to the administration of the study treatment.

In addition, all suspected adverse reactions considered "serious" entered into OnCore[®], will be reviewed and monitored by the Data and Safety Monitoring Committee on an ongoing basis and discussed at DSMC meetings, which take place every six weeks.

Adverse event reporting will continue until 24 months post-transplant, or until 90 days after the patient stops trial participation, if applicable.

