11.16 SAE Reports Associated with Study Stopping Rules

The following SAEs have a potential to trigger study stopping rules (see Section 8.7) and must be reported to the Study Chair within 24 hours:

- 11.16.1 aGVHD of grade IV
- 11.16.2 Severe cGVHD
- 11.16.3 Any organ toxicity of grade IV (using CTC Common Toxicity criteria version v4.0) that is judged to be related to withdrawal of immunosuppression, azacitidine, or DLI.
- 11.16.4 Any death judged to be related to fast immunosuppression withdrawal, azacitidine, or DLI.
- 11.16.5 Note: investigators must report any aGVHD grade IV, severe cGVHD, any organ grade IV toxicity or any death in patients undergoing immunosuppression withdrawal to the Study Chair within 24 hours. Judgment about contribution of withdrawal of immunosuppression to the reported severe event will be made by DSMC within 10 days.
- 11.16.6 Phone or fax reports of SAE's due within 24 hours to:
[REDACTED]

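### The percentages in the 8.7.2 safety table are not stopping probabilities: at the acceptable 20% SAE rate the table prints at most 8.2%, while the tabulated rule stops 25.1% of trials by patient 27

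*Combined protocol and SAP*

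**What the plan says.** Section 8.7.2 states that "A rate of SAEs of up to 20% is deemed acceptable in view of the potential benefit of the therapy". It then gives the rule in prose: "Accrual will stop if 3 patients with SAEs are observed in the first 3-6 patients undergoing the intervention", with 4 among the first 7-9 and 5 among the first 10-13 as the next two steps. The table that follows is introduced as displaying, for this rule, the smallest "number of SAEs for the study to be stopped at each accrual period and the probability of early stopping at the assumed SAE rate". Its limits are at least 3, 4, 5, 6, 7 and 8 SAE patients for bands 4-6, 7-9, 10-13, 14-17, 18-21 and 22-27. The last three bands appear only in the table. Each band carries a percentage range for true SAE rates of 15, 20 and 25%; at 20% the ranges run from 2.6-8.2% in the first band to 3.6-8.2% in the last. No cumulative stopping probability is given.

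The columns are headed by the number of patients on study, whereas the sentence counts patients undergoing the intervention. Section 7.1.2, on terminating the study, cites the stopping rules of 8.7.3 only. Section 8.7.3 has its own, much looser SAE row (for example at least 13 at 22-28 patients).

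**The concern.** A rule checked repeatedly as patients accumulate has a stopping chance that can only grow with n. The printed ranges do not grow: at 20% the upper ends go 8.2, 6.6, 6.9, 6.8, 6.6, 8.2%. So they cannot be the chance of having stopped by that point, and it has to be asked what they are.

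The table is the only statement of how this safety rule behaves. A monitoring committee, ethics board or sponsor reading it would conclude that a trial at the acceptable SAE rate is rarely halted, and also that the rule reacts weakly at 25%, where the largest printed value is 14.2%. If both impressions are wrong, nobody can judge from the protocol whether the limits are the ones they want.

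**Working it through.** **Inputs.** Limits r(n) from 8.7.2: 3 for n = 3-6, 4 for 7-9, 5 for 10-13, 6 for 14-17, 7 for 18-21, 8 for 22-27. True SAE rates p = 15, 20 and 25% as in the table; 30 and 40% added for illustration. Patients are taken as independent with a common p, and each counts once.

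**Step 1: reproduce the printed figures.** The formula that fits is the point probability P(X = r) = C(n, r) p^r (1 - p)^(n - r) at the first and last n of each band. At p = 0.20, n = 6, r = 3: 20 × 0.008 × 0.512 = 0.0819, printed 8.2%. At n = 27, r = 8 it is again 8.19%, printed 8.2%. Of the 36 printed values, 34 agree within 0.1 point; the largest gap is 0.21 (25%, n = 22: 8.69 against 8.9).

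**Step 2: a single look at an at-least limit.** This needs P(X ≥ r). At n = 6, p = 0.20: 1 - (0.2621 + 0.3932 + 0.2458) = 0.0989. Upper end of each band at 20%:

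| n | limit | printed | P(X = r) | P(X ≥ r) |
|---|---|---|---|---|
| 6 | 3 | 8.2% | 8.2% | 9.9% |
| 9 | 4 | 6.6% | 6.6% | 8.6% |
| 13 | 5 | 6.9% | 6.9% | 9.9% |
| 17 | 6 | 6.8% | 6.8% | 10.6% |
| 21 | 7 | 6.6% | 6.6% | 10.9% |
| 27 | 8 | 8.2% | 8.2% | 15.6% |

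The print is therefore too low even for one isolated look.

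**Step 3: the sequential rule.** Let f_n(k) be the chance of k SAE patients among the first n without having stopped. Then f_n(k) = (1 - p) f_(n-1)(k) + p f_(n-1)(k - 1), and any mass with k ≥ r(n) is removed and added to the stopped total. By hand for the first two bands at 20%: stopped by 6 is 0.0989. To stop in 7-9, a trial with 2 SAE patients at n = 6 (0.2458) needs at least 2 of the next 3 (0.104), and one with 1 (0.3932) needs all 3 (0.008). That adds 0.0256 + 0.0031 = 0.0287, so 0.1276 by patient 9. Continuing gives the cumulative chance of having stopped:

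| True rate | by 6 | by 9 | by 13 | by 17 | by 21 | by 27 | largest printed |
|---|---|---|---|---|---|---|---|
| 15% | 4.7% | 5.9% | 7.2% | 8.0% | 8.7% | 9.9% | 4.2% |
| 20% | 9.9% | 12.8% | 16.1% | 18.7% | 20.8% | 25.1% | 8.2% |
| 25% | 16.9% | 22.1% | 28.4% | 33.6% | 37.8% | 46.1% | 14.2% |

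At 30% and 40% the chance by patient 27 is 67% and 93%. A simulation of the 20% case also gave 25.1%.

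**Step 4: other ways of applying the rule, at 20%.** Starting at patient 3 or 4, or checking only at band ends, leaves 25.1%, because the limit is constant within a band. The prose bands alone (to patient 13) give 16.1%. Looking only at the start of each band (4, 7, 10, 14, 18, 22) gives 10.9%. Adding the 8.7.3 SAE limits leaves 25.1%. None is as low as 8.2%.

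**The case against.** The strongest reply is that the table gives a separate range for each band and never offers 8.2% as an overall risk. Differencing the 20% row gives the chance of stopping within each band: 9.9, 2.9, 3.3, 2.6, 2.1 and 4.3%. Five of the six printed upper ends lie above these, and only the first (8.2 against 9.9) is too low. It is fair that 8.2% and 25.1% answer different questions. But this does not rescue the table. The first band is understated at all three rates (4.2 against 4.7, 8.2 against 9.9, 13.2 against 16.9), and the printed figures match neither the within-band chance nor the single-look chance. They are exact-count probabilities under a label that says otherwise.

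A second reply is that the sentence stating the rule ends at patient 13, so 25.1% relies on bands found only in the table. That is correct, and the 16.1% figure should stand beside it. The table is introduced as displaying the same rule, so using all six bands is the natural reading.

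A reader might go further and infer that, because the columns count patients on study, late SAEs would be compared with a limit that has already moved on, so that most would be missed. The documents do not support this. The sentence ties the count to the first n treated patients, and the table is presented as showing that rule. How many events would be affected depends on SAE timing the documents do not give. With 67 patients over 24 months, patient 28 enrols at about month 10. The share of SAEs in the first 27 patients falling after that is 15% if events are uniform over months 0-3 from enrolment, 31% over 0-6, 58% over 0-12 and 95% over 6-24. Such events would still meet the 8.7.3 SAE row, though it is loose: alone it stops 0.6% of trials at 20%. What stands is a mismatch of labels. Low-risk ALL patients and those with Grade III-IV GVHD are on study without study therapy, so the two counts differ.

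**Conclusion.** The point holds for the printed probabilities. The percentages in 8.7.2 are exact-count binomial probabilities, not stopping probabilities, and they understate how often the rule halts accrual. At the acceptable 20% rate the tabulated rule stops 25.1% of trials by patient 27, about three times the largest printed value (25.1 / 8.2 = 3.1).

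These figures assume independent patients with a common SAE rate, all six tabulated bands, and an SAE counted against the first n treated patients whenever it occurs.

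This does not show that the limits are wrong. The protocol sets no target for the chance of stopping at an acceptable rate, and one in four may be a price the sponsor wishes to pay for a 93% chance of stopping at 40%. The column label and the cross-reference in 7.1.2 are matters of clarification only.

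**What to change.** Keep every limit in 8.7.2. Replace the printed ranges with the cumulative values by patient 6, 9, 13, 17, 21 and 27 at 15, 20 and 25%, and add the values by patient 27 at 30 and 40%. State in the text that a trial at the acceptable rate has about a one-in-four chance of stopping by patient 27.

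As clarification, head the columns with the first n patients undergoing the intervention, to match the sentence, so that an SAE counts against the patient's own cohort. Have 7.1.2 cite 8.7.2 as well as 8.7.3.

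The cost is one set of numbers, one sentence, one label and one cross-reference, with no change to patients, visits or limits. The downside is that the 25% becomes explicit. The sponsor must either accept it or choose different limits knowingly.
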